9. STUDY TIMELINES

- *Describe the duration of an individual's participation in the study*
- *Describe the duration anticipated to enroll all study subjects*
- *The estimated date of study completion*

Subjects enrolled in this study will participate on the day of their scheduled upper endoscopic procedure, which will last for about 1 hour. Subsequently, these patients will be followed for a period of about 1 year via their electronic medical

records. After the day of the initial procedure, they will not be contacted for study related purposes. |

10. ENDPOINTS

- *Describe the primary and secondary study endpoints*
- *Describe any primary or secondary safety endpoints*

The following outcomes will be measured:

- Primary Outcome: The time for image interpretation in each arm will be compared. Time will be a surrogate for ease of interpretation. Time will be recorded from start of image interpretation to the end of image interpretation. Length of Barrett's will be taken into account (time per cm of Barrett's) when comparing this outcome between patients and procedures.
- Secondary Outcome: Biopsy yield of dysplasia/diagnosis of dysplasia (dysplasia present versus not) of IRIS biopsies (double laser mark) will be compared to VLE without IRIS biopsies (single laser mark) and random biopsies.
- Secondary Outcome: The number of biopsies will be compared among all groups. |

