4. OBJECTIVE(S)/SPECIFIC AIMS AND HYPOTHESES

- *A concise statement of the goal(s) of the current study.*
- *The rationale for and specific objectives of the study.*
- *The goals and the hypothesis to be tested should be stated.*

1. To determine if IRIS facilitates interpretation of VLE images compared to VLE alone
2. To determine if IRIS increases the diagnostic yield for dysplasia compared to VLE alone and random biopsies
3. To determine if IRIS decreases the number of biopsies needed to identify dysplasia compared to VLE alone and random biopsies |

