Both VLE and IRIS imaging are being performed as standard of care. However, randomization of the order allows for comparison of the two. Regions of interest (ROI) will be recorded using a full scan and recorded on the case report form. The time to identification of ROIs will also be recorded (from start of image interpretation to the end). Each group will then cross over such that the VLE without IRIS group will then have IRIS turned on ROI will then be recorded for each group based on full scans. A consensus ROI will be recorded based on the two exams. Only one ROI per centimeter will be allowed to avoid overlapping of laser marks. In addition VLE without IRIS and IRIS marks within 75 frames of each other or 2 hours (on a clock face orientation) will be considered the same target.

Laser marking will then be performed. A double laser mark will be applied to all IRIS ROIs. A single laser mark will be applied to VLE ROIs. Targeted biopsies will be taken of all laser marks and placed in separate biopsy jars. Biopsies will be taken in between the laser marks for double laser marked areas. For single laser marks, biopsies will be taken on either side of the laser mark. Resection of visible

lesions will then occur per standard of care (if present) followed by random biopsies of the segment. Random biopsies are pinch biopsies every 1 cm the length of the Barrett's in a 4 quadrant fashion per gastrointestinal society guidelines. This is all per standard of care. There are no additional research biopsies being performed outside this study. The targeted biopsies are based on the VLE features that are suspicious for dysplasia and thus standard of care. The other biopsies being performed here are random biopsies which are also being performed for standard of care. Biopsied samples will be stored per standard of care procedures per the pathology department. They will not be stored for future research purposes.

Following each procedure, the physician will be asked a series of Likert Scale questions to assess the utility of IRIS in that procedure, including how it impacts their confidence in image interpretation, their ability to assimilate data more easily and quickly, and their overall perception of the technology.

Although the VLE with IRIS and VLE without IRIS are being performed as standard of care, all adverse events will be recorded and reported to the IRB.

All data will be entered into a central encrypted REDCap database housed within the Northwell server.

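### Dysplasia yield is grouped by laser mark, with no visible rule crediting a target named by both reads, and the planned Fisher test ignores that the groups come from the same patients

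*Combined protocol and SAP*

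**What the plan says.** Section 10 defines the yield outcome as dysplasia present or absent and forms its groups by mark: "IRIS biopsies (double laser mark) will be compared to VLE without IRIS biopsies (single laser mark) and random biopsies". It does not say whether the unit is the patient or the biopsy.

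Section 11 describes how the marks arise; section 2 gives the same account. Each patient has both reads in randomised order: "Each group will then cross over such that the VLE without IRIS group will then have IRIS turned on". Overlap is foreseen, since "A consensus ROI will be recorded based on the two exams" and IRIS and VLE "marks within 75 frames of each other or 2 hours (on a clock face orientation) will be considered the same target". The marking rules are "A double laser mark will be applied to all IRIS ROIs" and "A single laser mark will be applied to VLE ROIs". No more than one region of interest is allowed per centimetre. Double-marked sites are biopsied between the two marks, whereas "For single laser marks, biopsies will be taken on either side of the laser mark".

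Aim 3 in section 4 is "To determine if IRIS decreases the number of biopsies needed to identify dysplasia compared to VLE alone and random biopsies". Section 8 describes the yield outcome as dysplasia found in each arm and expects little difference. Section 12 plans Fisher's exact test for categorical variables and gives presence of dysplasia as its example.

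**The concern.** The mark is being used as a label for the imaging method, but a target that both reads identify belongs to both methods. If it carries the double mark and is counted by mark, the comparison becomes everything IRIS found against only what VLE alone found. Two reads of equal performance could then look different on Aim 2, and the more they agree, the larger the false difference. The number of biopsies and the biopsies needed per dysplasia (Aim 3) depend on the same grouping.

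The second problem does not depend on how shared targets are marked. IRIS, VLE and random biopsies all come from the same patients, and Fisher's test treats them as independent groups.

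**Working it through.** **Plan's own figure.** The documents give no expected yield, overlap or power for this outcome. The only sample-size figure, 94 in section 8, concerns interpretation time and has no bearing here. (With difference 2 min, SD 3 min, two-sided 5% and 90% power, 2 × [3 × (1.960 + 1.282)/2]² = 47.28 per group, so 94 is reproduced to within rounding.)

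**How a shared target is marked.** Section 11 double-marks all IRIS regions without exception; the VLE sentence does not say all. Nearby marks are one target, and the limit of one region per centimetre leaves no evident room for a second mark at the same site. A shared target is therefore most naturally double-marked and, under section 10, an IRIS biopsy. This is an inference.

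**Direction.** Let V be the patients with dysplasia in any VLE-named target, and S those among them whose dysplastic VLE targets are all shared. The mark-coded VLE count is V − S; the IRIS count is unchanged. Since S ≥ 0, the VLE proportion over all patients cannot rise. In 2,000 simulated trials it rose in none. The per-biopsy rate rose in 1,000 and fell in 1,000. A per-patient rate restricted to patients with a single mark rose in 464.

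**Size on assumed inputs.** Both reads truly detect dysplasia in the same proportion y of N patients, with one dysplastic target per positive patient and a fraction q of VLE targets shared. Mark-coded VLE count = N·y·(1 − q); two-sided Fisher test.

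| N, y | IRIS | VLE at q = 25 / 50 / 75% | Fisher p |
|---|---|---|---|
| 200, 20% | 40 | 30 / 20 / 10 | 0.24 / 0.007 / <0.0001 |
| 200, 10% | 20 | 15 / 10 / 5 | 0.48 / 0.09 / 0.003 |
| 94, 20% | 19 | 14 / 9–10 / 5 | 0.44 / 0.06–0.11 / 0.004 |

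With two targets per positive patient, shared independently, the VLE count is N·y·(1 − q²). At N = 200, y = 20% and q = 50% that is 40 × 0.75 = 30, p = 0.24.

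The sign can also reverse. Suppose, in 200 patients, VLE finds 40, IRIS 35 and both 25, with one target each. Mark coding shows IRIS 35 versus VLE 40 − 25 = 15, Fisher p = 0.004 in favour of IRIS. The paired comparison has 10 IRIS-only and 15 VLE-only patients, exact McNemar p = 0.42.

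**Test alone, shared targets credited to both reads.** Assume 25 patients found by both, 15 by IRIS only and 5 by VLE only, out of 200. The totals are 40 versus 30. Fisher gives p = 0.24; exact McNemar on 15 versus 5 gives p = 0.041.

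**Biopsies per dysplasia (Aim 3).** Assume 100 targets per read, 50 shared and 20 dysplastic per read. Shared and unshared targets have equal yield (20% each), or shared are richer (30% versus 10%), or poorer (10% versus 30%). VLE-only targets then hold 10, 5 or 15 dysplasias.

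- One biopsy per mark: IRIS 100/20 = 5.0. Mark-coded VLE 50/10 = 5.0, 50/5 = 10.0 or 50/15 = 3.3. VLE with shared credit 100/20 = 5.0.
- Two per single mark, one per double mark: IRIS 5.0. Mark-coded VLE 100/10 = 10.0, 100/5 = 20.0 or 100/15 = 6.7. VLE with shared credit (100 + 50)/20 = 7.5.

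For the raw count, the mark-coded VLE group lacks the 50 shared biopsies: 50 instead of 100 in the first case, 100 instead of 150 in the second. The IRIS count is not inflated.

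**The case against.** The strongest reply is that nothing in the documents says a shared target counts for IRIS only. The authors foresaw overlap, and the crediting rule may sit in Figure 2 or the case report form, neither of which is shown. That stands: what is established is that the visible text gives no rule, and the direction follows from a natural reading of it.

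A reader might also infer that VLE yield must fall on every measure. The documents do not support this. Section 10 fixes no unit, and per biopsy, or among single-marked patients only, the direction is open. Even per patient over all patients, the count may be unchanged.

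Nor does crediting by read make the comparison perfectly clean. Single and double marks are sampled differently, so a shared biopsy credited to VLE was not taken as a VLE-only biopsy would be. If the one-per-centimetre limit applies across reads, a distinct nearby target may never be biopsied, and no crediting rule recovers it.

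Finally, section 8 speaks of arms. If arms mean the randomised first reads, an unpaired test is right for that comparison. The objection to Fisher's test applies to the groups of section 10, which are within patient.

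**Conclusion.** The point holds as a should-fix matter, with medium confidence. Section 10 groups by mark, the visible text has no crediting rule for shared or consensus targets, and Fisher's test does not match the within-patient groups. If shared targets count for IRIS only, VLE per-patient yield over all patients can be lowered or left unchanged, never raised.

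The size rests wholly on assumed overlap, detection and targets per patient. The false difference is marked at high overlap and weak at low overlap. For Aim 3 it is tempting to say that mark coding is neutral when shared and unshared targets have equal yield; that holds only with equal numbers of biopsies per mark, which section 11 does not establish. It would also be wrong to read this as undermining the trial's main result: interpretation time, the primary outcome, is untouched.

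**What to change.** In sections 10 and 12:

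- Define modality by the read that named the region, not by the mark. Classify each target as IRIS-only, VLE-only or shared, and credit shared targets and their biopsies to both reads. State how a consensus region is credited, and whether the frame and clock-hour limits must both hold, since this decides which targets are shared.
- Make the patient the unit, with all patients as denominator. Compare presence of dysplasia between reads with McNemar's test, and likewise each read against random biopsies.
- Report results by randomised read order, because the second read may be influenced by the first.
- For biopsy counts and biopsies per dysplasia, note that single and double marks are sampled differently and report target counts alongside. If a per-biopsy yield is given, allow for several biopsies per patient.

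Reconcile the wording on arms in section 8 with section 10. If randomised first reads are also compared, an unpaired test is right for that analysis.

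The cost is wording and a little more analysis. Section 11 already records regions for each exam and puts targeted biopsies in separate jars. Check that Figure 2 does not already give a rule, and that the case report form links each region's read of origin to its jar. Marking and biopsy procedures do not change.

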11. RESEARCH PROCEDURES

- *Include a detailed description of all procedures to be performed on the research subject and the schedule for each procedure.*
- *Include any screening procedures for eligibility and/or baseline diagnostic tests*
- *Include procedures being performed to monitor subjects for safety or minimize risks*
- *Include information about drug washout periods*
- *If drugs or biologics are being administered provide information on dosing and route of administration*
- *Clearly indicate which procedures are only being conducted for research purposes.*
- *If any specimens will be used for this research, explain whether they are being collected specifically for research purposes.*
- *Describe any source records that will be used to collect data about subjects*
- *Indicate the data to be collected, including long term follow-up*

This is a prospective randomized clinical trial examining how IRIS (Intelligent Real-time Image Segmentation) affects biopsy patterns in VLE (Volumetric laser endomicroscopy). Patients will undergo a VLE exam with and without IRIS per the standard of care. All patients regardless of the study participation in this study would receive VLE with and without IRIS clinically. Thus randomization into a particular order will not require more procedure time. They will be randomized into VLE without IRIS first vs VLE with IRIS first. Subjects will be randomized with the BUDDY Randomization System provided for use by the Northwell Health Biostatistics Unit. Randomization will occur before the procedure starts. Randomization will be stratified based on prior diagnosis of dysplasia. The order the patient is randomized to will be recorded on the case report form. There will be concealed allocation as the study coordinator performing the randomization will not know the order of the next allocation.

Both VLE and IRIS imaging are being performed as standard of care. However, randomization of the order allows for comparison of the two. Regions of interest (ROI) will be recorded using a full scan and recorded on the case report form. The time to identification of ROIs will also be recorded (from start of image interpretation to the end). Each group will then cross over such that the VLE without IRIS group will then have IRIS turned on ROI will then be recorded for each group based on full scans. A consensus ROI will be recorded based on the two exams. Only one ROI per centimeter will be allowed to avoid overlapping of laser marks. In addition VLE without IRIS and IRIS marks within 75 frames of each other or 2 hours (on a clock face orientation) will be considered the same target.

Laser marking will then be performed. A double laser mark will be applied to all IRIS ROIs. A single laser mark will be applied to VLE ROIs. Targeted biopsies will be taken of all laser marks and placed in separate biopsy jars. Biopsies will be taken in between the laser marks for double laser marked areas. For single laser marks, biopsies will be taken on either side of the laser mark. Resection of visible

lesions will then occur per standard of care (if present) followed by random biopsies of the segment. Random biopsies are pinch biopsies every 1 cm the length of the Barrett's in a 4 quadrant fashion per gastrointestinal society guidelines. This is all per standard of care. There are no additional research biopsies being performed outside this study. The targeted biopsies are based on the VLE features that are suspicious for dysplasia and thus standard of care. The other biopsies being performed here are random biopsies which are also being performed for standard of care. Biopsied samples will be stored per standard of care procedures per the pathology department. They will not be stored for future research purposes.

Following each procedure, the physician will be asked a series of Likert Scale questions to assess the utility of IRIS in that procedure, including how it impacts their confidence in image interpretation, their ability to assimilate data more easily and quickly, and their overall perception of the technology.

Although the VLE with IRIS and VLE without IRIS are being performed as standard of care, all adverse events will be recorded and reported to the IRB.

All data will be entered into a central encrypted REDCap database housed within the Northwell server.

Expert pathologists who specialize in gastrointestinal pathology will read the histology. A second gastrointestinal pathologist will confirm any histologic diagnosis of dysplasia. This is the standard of care at Northwell Health and academic medical centers per gastrointestinal society guidelines.

All procedures (upper endoscopy, volumetric laser endomicroscopy, and IRIS enhanced VLE) will be performed as standard of care. The prospective data collection and initial randomization of order of use of IRIS will be the research component. All data collected will be de-identified before being transferred into a

database. This will be kept in a safe place that is only accessible to the research team.

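### The IRIS-versus-VLE yield comparison rests on marks set after both displays were read, with no stated credit for shared targets; a first-read comparison by randomized order should be added

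*Combined protocol and SAP*

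**What the plan says.** Section 4 aims to compare the dysplasia yield of IRIS with that of VLE alone and of random biopsies.

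Section 11 sets the sequence. The order of the two displays is randomized, and ROIs and reading time are recorded on a first full scan. Then "Each group will then cross over such that the VLE without IRIS group will then have IRIS turned on", and "ROI will then be recorded for each group based on full scans". Next, "A consensus ROI will be recorded based on the two exams". Laser marking follows only after that. "A double laser mark will be applied to all IRIS ROIs"; VLE ROIs get a single mark. At most one ROI per centimetre is kept, and marks from the two displays within 75 frames of each other "or 2 hours (on a clock face orientation) will be considered the same target". Biopsies of the marks go into separate jars.

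Section 10 defines the secondary yield outcome by mark type: dysplasia present or absent in double-mark biopsies, against single-mark biopsies and random biopsies. Section 8 describes the same outcome by arm and expects little difference. Section 12 names the Fisher exact test for dysplasia and the Student t-test for continuous outcomes.

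**The concern.** Two features separate the mark-type comparison from the aim in section 4.

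- **Carryover.** In the IRIS-first order, the VLE ROIs are recorded after IRIS has been displayed; in the other order the reverse holds. No masking or separate second reader is described. Section 11 says that after each procedure "the physician will be asked a series of Likert Scale questions to assess the utility of IRIS in that procedure", which suggests one reader but does not say so. No section limits the yield outcome to first-read ROIs.
- **Credit.** The merging rule says when two marks are one target. It does not say which display that target counts for. A shared target is an IRIS ROI (double mark) and also a VLE ROI (single mark).

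Because section 8 expects only a small difference in yield, the crediting rule could matter more than the true difference between displays.

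**Working it through.** **1. The plan's own figure.** Section 8 gives 94 patients (47 per group) for time. Inputs: means 5 and 3 min (difference 2), SD 3 (reading the plus-or-minus as an SD), two-sided 5%, power 90%. Per group: n = 2 × [3 × (1.960 + 1.282) / 2]² = 47.3. This matches 47 (48 when rounded up); a t-test has 89.2% power at 47 per group. The figure is thus a calculation for two independent groups, which fits one read per patient.

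**2. Yield model.** All inputs here are assumptions. Let b, d and s be the numbers of dysplastic targets that independent looks would find with IRIS only, VLE only and both. Half the patients are in each order. Let c1 be the chance that an IRIS second read keeps a VLE-only target, and c2 the chance that a VLE second read keeps an IRIS-only target. The true difference is b − d.

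- Shared targets credited to both: (s + b + c1·d/2) − (s + d + c2·b/2) = (b − d) + (c1·d − c2·b)/2.
- Shared targets credited to IRIS only: (s + b + c1·d/2) − (d − c1·d/2) = s + b − d + c1·d.

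**3. Target counts.**

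| b, d, s | c1, c2 | True | Credited to both | IRIS only |
|---|---|---|---|---|
| 10, 10, 10 | 0, 0 | 0 | 0 | +10 |
| 10, 10, 10 | 0.5, 0.5 | 0 | 0 | +15 |
| 6, 14, 10 | 0.5, 0.5 | −8 | −6 | +9 |
| 10, 10, 10 | 0.8, 0.2 | 0 | +3 | +18 |
| 10, 10, 10 | 0.2, 0.8 | 0 | −3 | +12 |
| 14, 6, 0 | 0.8, 0.2 | +8 | +9 | +12.8 |

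With equal carryover c, crediting both gives (b − d)(1 − c/2), which shrinks toward no difference. With unequal carryover it can move either way.

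**4. Per-patient scale.** Assume 200 patients with at most one dysplastic target each: 5 IRIS-only, 5 VLE-only, 10 shared. IRIS-only credit gives 15 against 5 (Fisher p = 0.036); crediting both gives 15 against 15 (p = 1.0). The p-values are only illustrative, since both counts come from the same patients.

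**5. Per-biopsy scale.** Assume 50 IRIS-only, 50 VLE-only and 50 shared targets, with 20% of the first two groups dysplastic and a proportion p of the shared ones. IRIS-only credit gives (10 + 50p)/100 − 10/50 = (p − 0.20)/2. At p = 0.20 this is 20/100 against 10/50, no difference. A gap appears only if shared targets differ in dysplasia rate.

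**6. First-read contrast.** By randomized order, the target difference is (s + b)/2 − (s + d)/2 = (b − d)/2, with no credit or carryover term, provided every first-read ROI is biopsied. For a per-patient proportion at 80% power and two-sided 5%, the detectable difference solves δ = 1.96·√(2p̄(1 − p̄)/n) + 0.842·√([p1(1 − p1) + p2(1 − p2)]/n), where p2 = p1 + δ and p̄ is their mean:

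| Assumed base yield | 47 per arm | 100 per arm |
|---|---|---|
| 10% | 23.6 points | 15.0 points |
| 20% | 26.9 points | 17.9 points |
| 30% | 28.3 points | 19.3 points |

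**The case against.** The strongest reply is that the plan does imply a crediting rule: every IRIS ROI is double-marked, merged marks are one target, and section 10 counts double marks as IRIS. That is the most natural reading, and it stands as such. But it is a marking instruction. Used as the analysis rule, it leaves VLE only the targets IRIS did not flag, which is not the yield of VLE alone. The single-mark sentence could also cover a shared target.

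A reader might infer a fixed direction of bias, either always toward IRIS or always toward no difference. The documents support neither. The direction depends on the crediting rule, on whether carryover is equal in both orders, and on whether yield is per patient, per target or per biopsy, which section 10 does not settle.

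A reader might also infer that the primary time outcome is contaminated. The text points the other way. The sentence "The time to identification of ROIs will also be recorded (from start of image interpretation to the end") stands before the crossover, section 10 compares time in each arm, and the sample size and t-test are for independent groups. The mention in section 10 of comparing patients and procedures sits in a sentence about allowing for Barrett's length. One confirming sentence is enough.

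Finally, the first-read contrast is imprecise, and first-read ROIs dropped before marking have no targeted histology. Both points stand and should be stated in the plan. Figure 2 and the case report form are not available here and might settle some details.

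**Conclusion.** The concern holds for the secondary yield outcome. Followed as written, the mark-type comparison includes ROIs chosen after the other display was seen, if one physician does both reads, and no section states the credit for shared targets. On a count or per-patient scale, IRIS-only credit favours IRIS by the number of shared dysplastic targets even without carryover: +10 in the assumed example with no true difference. On a per-biopsy proportion the effect may be nil. If both displays are credited, any remaining carryover bias has no known direction. The sizes rest on assumed counts and carryover, since the documents give none.

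This should be fixed, but it does not undermine the primary outcome or its sample size. In section 8 both mean times are labelled as without IRIS; that is a separate wording error and does not change the sample size.

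**What to change.** **Sections 10 and 12, yield**

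- Add a per-patient comparison of dysplasia at ROIs identified on the first read, IRIS-first against VLE-first, by randomized order, as a difference with 95% confidence interval. Link each jar to the read that first identified its ROI.
- In the mark-type comparison, credit a shared target to both displays and present the comparison as descriptive.
- State that first-read ROIs dropped by the consensus or one-ROI-per-centimetre rule have no targeted histology, and report their number by arm. State also that merging, and a mark type set after the second read, leave some carryover.

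**Minor**

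- Confirm in one sentence that the primary time is first-read time per centimetre, by randomized order.
- Correct the label on one of the two means in section 8.

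**Cost.** Mostly wording. ROIs are already recorded before and after the crossover, jars are separate, and "The order the patient is randomized to will be recorded on the case report form". A field linking jar to read may be needed; the form would have to be checked. No patients or biopsies are added. The downside is precision: the first-read contrast detects only differences of about 15 to 28 points at 47 to 100 per arm, for an assumed 10–30% yield. It should be labelled an estimate, not a powered test.

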8. NUMBER OF SUBJECTS

- *Indicate the total number of subjects to be accrued locally. If applicable, distinguish between the number of subjects who are expected to be pre-screened, enrolled (consent obtained), randomized and complete the research procedures.*
- *If your study includes different cohorts, include the total number of subjects in each cohort.*
- *If this is multisite study, include total number of subjects across all sites.*

This is a multi-site randomized trial with an anticipated enrollment of 200 patients. We anticipate adding up to 3 other sites. Half of all patients should have a prior diagnosis of dysplasia to ensure a sample that has an adequate number of dysplastic patients.

The primary outcome will be time to interpretation of a VLE scan with and without IRIS. Dysplasia detected in each arm and number of biopsies are secondary outcomes and not expected to be that much different as expert VLE users will be involved in the study. The expected mean time for a VLE without IRIS is 5 min +/- 3 min. The mean time for a VLE without IRIS (standard) is 3 min. With a CI of 95% and power of 90%, the sample size for 1:1 randomization is 94 (47 in each group). Our sample size is 200 to allow for screen failures.

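### The rule matching IRIS and VLE targets joins its two tolerances with 'or', so closeness on one axis alone makes two marks the same target in the secondary comparisons

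*Combined protocol and SAP*

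**What the plan says.** Section 11 describes two reads of each patient, IRIS off and IRIS on in randomized order, and says that "ROI will then be recorded for each group based on full scans". It continues: "A consensus ROI will be recorded based on the two exams". Two spacing rules follow. The first is "Only one ROI per centimeter will be allowed to avoid overlapping of laser marks". The second is the matching rule, under which VLE-without-IRIS and "IRIS marks within 75 frames of each other or 2 hours (on a clock face orientation) will be considered the same target". Section 2 gives the matching rule in the same words.

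The next step is "Laser marking will then be performed". IRIS ROIs receive a double mark and VLE ROIs a single mark, and "Targeted biopsies will be taken of all laser marks and placed in separate biopsy jars".

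Section 10 builds a secondary outcome on the mark type: dysplasia yield of "IRIS biopsies (double laser mark) will be compared to VLE without IRIS biopsies (single laser mark) and random biopsies". It also compares the number of biopsies among the groups. Section 8 confirms the rank of these outcomes: "Dysplasia detected in each arm and number of biopsies are secondary outcomes". Section 12 names Fisher exact tests and t-tests. It defines no target-level variable and does not say how a target found on both reads is counted.

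**The concern.** Frame number gives the position along the esophagus, and clock hour gives the position around it. Two marks are at the same place only if they agree on both. Joined by 'or', each tolerance is sufficient alone, so the rule treats as one target many pairs of marks that are plainly at different places.

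The rule decides which targets count as found by both reads and which by one modality only. That classification underlies aims 2 and 3 in section 4 and the yield and biopsy-number outcomes in section 10. If unrelated IRIS and VLE sites are classed as shared, the two modalities look more alike in what they target than they were. Section 8 anticipates up to 3 other sites, so there is a further risk that some operators apply the words literally and others assume that both tolerances are needed. Target classification would then differ by site.

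**Working it through.** The documents give no derived figure for this rule, so there is none to reproduce. The check has three parts.

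**1. Geometry, from section 3.** The scan has 1,200 frames over 6 cm, and the balloons are 14, 17 or 20 mm in diameter.
- Frames per cm: 1,200 / 6 = 200. The frame tolerance is 75 / 200 = 0.375 cm.
- Clock tolerance: 2 hours is 2/12 of 360 degrees = 60 degrees. The arc is pi x diameter / 6 = 7.3, 8.9 or 10.5 mm.
- Opposite walls (12 and 6 o'clock) are pi x diameter / 2 apart around the wall, or 22 mm on the 14 mm balloon and 31 mm on the 20 mm balloon. In the same frame, the rule makes them one target.
- Two marks at the same clock position are one target at any distance along the scan, up to the full 6 cm.

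**2. Chance merging of two unrelated marks.** Assumptions (not in the documents): the marks are placed independently and uniformly along a length L and around the clock. L = 6 cm is a full scan. L = 3 cm is a shorter segment that meets the entry criterion of more than 2 cm.
- Frame match: a = 1 - (1 - 0.375/L)^2. For 6 cm, 1 - 0.9375^2 = 0.121. For 3 cm, 1 - 0.875^2 = 0.234.
- Clock match: p = 4/12 = 0.333 if the tolerance is plus or minus 2 hours, or 2/12 = 0.167 if 2 hours is a total window.
- Either tolerance met: a + p - ap. Both met: ap.

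| Reading of 2 hours | L | Either ('or') | Both ('and') |
|---|---|---|---|
| plus or minus 2 | 6 cm | 0.121 + 0.333 - 0.040 = 0.414 | 0.040 |
| plus or minus 2 | 3 cm | 0.234 + 0.333 - 0.078 = 0.490 | 0.078 |
| total window | 6 cm | 0.121 + 0.167 - 0.020 = 0.268 | 0.020 |
| total window | 3 cm | 0.234 + 0.167 - 0.039 = 0.362 | 0.039 |

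A simulation of 2 million pairs (plus or minus 2 hours) gave 0.414 and 0.490 for 'or', and 0.040 and 0.078 for 'and'. Under plus or minus 2 hours, the share of 'or' merges that agree on one axis only is 1 - 0.040/0.414 = 90% on 6 cm and 1 - 0.078/0.490 = 84% on 3 cm.

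**3. Does the one-ROI-per-centimeter limit repair this?** Section 11 does not say whether the limit applies within each read or across both.
- If it applies within a read, it does not restrict how far an IRIS mark lies from a VLE mark, and the table stands.
- If it applies across reads and means at least 1 cm (200 frames) apart, the 75-frame clause can never be met. The clock clause still merges a third of unrelated pairs (p = 0.333), and requiring both would merge none.

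On neither reading does the limit deal with marks far apart at a similar clock position.

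**The case against.** The strongest reply is that this is loose wording. A tolerance on both axes may well have been meant. Few endoscopists would call marks at opposite ends of a scan one target, and the rule follows a consensus step that involves judgment. That is a fair account of likely practice. But no readable text requires both tolerances, and the same wording appears twice. The flow diagram (Figure 2) is not shown and could bear on this step, so the absence is of readable text only.

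The percentages also have limits. The two reads are of the same patient in the same procedure, so real marks are correlated and often are the same site. The rates apply only to pairs that are not. A reader might infer that 41% or 49% of targets would be miscounted; the calculation does not show that.

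A reader might also infer that a wrongly merged site goes without a targeted biopsy, because the matching rule comes before laser marking in section 11. That rests on sentence order alone. The same section says that all IRIS ROIs and the VLE ROIs are marked and that all marks are biopsied, and the matching rule can be read as a counting rule. Loss of a biopsy is possible but not shown.

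Nor can a biased yield comparison in a known direction be inferred. A shared target is an IRIS ROI and so arguably receives a double mark, but how it is credited in the comparison is not stated. If yield is analyzed per patient, as dysplasia present or not, it is less sensitive to matching than counts per target.

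Finally, these are secondary outcomes on which section 8 expects little difference. That limits the weight of the point but does not remove it, since two of the three aims depend on them.

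**Conclusion.** The concern holds for the classification of targets in the secondary outcomes. The rule as written makes agreement on one axis sufficient, and the document's own scan figures show that it then joins sites that are clearly distinct. For unrelated marks, under independent uniform placement, it merges 41% (6 cm) or 49% (3 cm) of pairs, against 4% or 8% if both tolerances are required. With 2 hours as a total window the figures are 27% and 36% against 2% and 4%. These rates illustrate how loose the rule is; they do not forecast error in the trial. The effect on yield or biopsy number cannot be estimated in size or direction. The primary outcome, interpretation time, and the sample size do not depend on the rule. The point should be corrected, but it does not threaten the main result.

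**What to change.** In section 12, define for the analysis that an IRIS ROI and a VLE ROI are the same target only if they are within 75 frames **and** within 2 clock hours, and state whether that means plus or minus 2. Apply the definition to the ROIs recorded on each read. State how a shared target is credited, for example counted once as found by both. Report any site that was merged before marking and not separately biopsied, because an analysis definition cannot supply histology that was never taken.

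Separately, the sponsor should reconcile the 'or' wording in sections 2 and 11 with the one-ROI-per-centimeter limit, and say whether that limit applies within or across reads. Where marks and biopsies are placed is left to the sponsor; nothing is proposed here on that.

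The cost is a short paragraph and agreed wording in two sections. The definition needs the frame and clock position of each ROI on each read. The existing rule already depends on these, but the case report form is not among the documents, so it should be confirmed that it records them.
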